6.1 Dose Limiting Toxicity Criteria

DLT will be evaluated during the first 28 days of the first cycle during the dose escalation portion of the trial. All toxicities will be graded using CTCAE v 4.03. The occurrence of any of the following toxicities will be considered a DLT, if judged by the Investigator to be possibly, probably or definitely related to therapy. Treatment modifications for DLT are shown in Table 11.

Hematologic:

- 1. Grade 4 hematologic toxicity.
- 2. Febrile Neutropenia, defined as absolute neutrophil count (ANC) < 1000/mm³ with a single temperature of >38.3° C (101° F) or a sustained temperature of >38° C (100.4° F) for more than 1 hour.
- 3. Grade 3 thrombocytopenia lasting >72 hours.
- 4. Grade 4 thrombocytopenia.

Non-Hematologic:

1. ≥Grade 3 non-hematologic toxicity, (excluding nausea, vomiting and/or diarrhea lasting <3 days and reversible with medical intervention).

- 2. Grade 3 non hematologic laboratory values, (excluding transient Grade 3 laboratory value abnormalities, hematologic and non-hematologic, reversible within 5 days and without necessity for medical intervention).
- 3. Listeremia: positive blood cultures(s) along with persistent (for 72 hours post dose) symptoms consistent with listeremia (e.g., fever and muscle aches, often preceded by diarrhea or other gastrointestinal symptoms).
- 4. \(\geq \) Grade 3 flu-like symptoms or cytokine release symptoms that persist for >24 hours after study treatment administration despite symptomatic treatment.

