11.4 Supportive Care Guidelines

11.4.1 Cytokine Release Symptoms

Cytokine release symptoms are a constellation of inflammatory symptoms resulting from cytokine elevations associated with T cell engagement and proliferation. Symptoms related to cytokine release may include constitutional symptoms such as fever, chills, rigors, fatigue, headache, nausea, vomiting, rash, tachycardia, hypotension and shortness of breath which usually presents several hours after the infusion and lasts for up to 24 hours. These symptoms are caused by an increase in cytokines such as TNF α , IFN γ and IL-6, all of which have been shown to occur after ADXS11-001 administration, resulting from the body's immune response to the therapy. Although, symptoms are often Grade 1-2 and transient, resolving with symptomatic management within 30 minutes to 1 hour, in rare instances (\sim 1%) Grade 3-4 hypotension has been seen. Therefore, close monitoring of blood pressure is strongly recommended at baseline, and during the post-infusion period. Increased levels of IL-6have been strongly associated with capillary leak which manifests as hypotension due to the cytokines involved. We have observed elevated IL-6 levels after infusion of ADXS11-001, with peak levels occurring 2-4 hours after infusion. Emerging evidence indicates that IL-6 antagonists, such as tocilizumab, have demonstrated good results in treating cytokine-induced hypotension [20-23] and are therefore recommended for cases of severe hypotension refractory to supportive care (e.g., fluids and/or pressors).

The management of cytokine release symptoms and guidelines for subsequent treatment for subjects who have experienced these AEs are shown in Table 9.

Table 9 Recommended Management Guidelines for Adverse Events Associated with Cytokine Release

Toxicity	NCI CTCAE Grade or Severity	Treatment	Modification for Subsequent infusions
Hypotension	1 Mild	Supportive care	Increase pretreatment IV fluids (e.g., 500 ml -1L normal saline)
All other cytokine release symptoms (e.g. chills, rigors, fever, nausea, vomiting)	1	Supportive care	No modification

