Hypotension	2 Moderate	 Fluids and 1 dose of pressor (e.g. 0.3 mg epinephrine IM) Increase monitoring of vital signs If hypotension persist for more than one hour consider low dose corticosteroids (e.g. hydrocortisone 100 mg IV over 30 seconds 	 Extend infusion time to 2 hours. Increase pretreatment IV fluids (e.g. 500 ml -1L normal saline) Incorporate Glucocorticoid- Hydrocortisone or equivalent- 50 mg, IV, as premedication
All other cytokine release symptoms (e.g. chills, rigors, fever, nausea, vomiting)	2	Appropriate supportive care measure	 Extend infusion time to 2 hours. Consider increasing doses of prophylactic medications
Hypotension	3 Severe	 Fluids, high dose pressors (e.g. Dopamine 10 μg/kg/min) +1 dose tocilizumab*(4mg/kg over 1 hour) If hypotension worsens or is unresponsive to above measures, administer corticosteroids If the subject's condition does not improve or stabilize within 24 hours of the tocilizumab dose, administration of a second dose of tocilizumab +/- corticosteroids should be considered. 	Discuss with Sponsor

Toxicity	NCI CTCAE Grade or Severity	Treatment	Modification for Subsequent infusions
All other cytokine release symptoms (e.g. chills, rigors, fever, nausea, vomiting)	3	Appropriate supportive care measures	 Extend infusion time to 2 hours. Consider increasing doses of prophylactic dose of NSAID, or antiemetic as appropriate
Hypotension/ Organ toxicity, mechanical ventilation	4 Life threatening	 Vigilant supportive care Fluids High dose pressors, Tocilizumab (4mg/kg over 1 hour) +/- corticosteroids (hydrocortisone 100 mg IV infused over 30 seconds administered every 2 hours until symptoms resolve to <grade 1)<="" li=""> </grade>	Permanently discontinue

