11.5 Management of Infusion Reactions

While there is some overlap between infusion reactions symptoms and cytokine release symptoms, infusion reactions symptoms typically occur during the infusion, while cytokine release symptoms typically occur after the infusion and are mediated by a different mechanism of action. Signs/symptoms of infusion reactions may include: allergic reaction/hypersensitivity (including drug fever); arthralgia (joint pain); bronchospasm; cough; dizziness; dyspnea (shortness of breath); fatigue (asthenia, lethargy, malaise); headache; hypertension; hypotension; myalgia (muscle pain); nausea; pruritic/itching; rash/ desquamation; rigors/chills; sweating (diaphoresis); tachycardia; tumor pain (onset or exacerbation of tumor pain due to treatment); urticaria (hives, welts, wheals); and vomiting.

Table 10 below shows the management guidelines for subjects who experience an infusion reaction associated with administration of ADXS11-001.

Table 10 Recommended Management Guidelines for Infusion Reactions

NCI CTCAE Grade	Management
Grade 1	
Mild reaction; infusion interruption not indicated; intervention not indicated	Increase monitoring of vital signs as medically indicated until the subject is deemed medically stable in the opinion of the Investigator.
Grade 2	
Requires infusion interruption but responds promptly to symptomatic treatment (e.g., antihistamines, NSAIDS, narcotics, IV fluids); prophylactic medications indicated for ≤24 hrs.	Stop Infusion and monitor symptoms. Additional appropriate medical therapy may include but is not limited to:
	the subject is deemed medically stable in the opinion of the Investigator. If symptoms resolve within one hour of stopping drug infusion, the infusion may be restarted at 50% of the original infusion rate. Otherwise dosing will be held until symptoms resolve and the subject should be premedicated for the next scheduled dose.
Grades 3 or 4	
Grade 3: Prolonged (i.e., not rapidly responsive to symptomatic medication and/or brief interruption of infusion); recurrence of symptoms following initial improvement; hospitalization indicated for other clinical sequelae (e.g., renal impairment, pulmonary infiltrates) Grade 4: Life-threatening; pressor or ventilatory support indicated	 Stop Infusion. Additional appropriate medical therapy may include but is not limited to:

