	6. Subjects who experience a Grade 4 reaction should be permanently discontinued from study. Subjects who experience a grade 3 reaction may be discontinued. Discussion with the Sponsor is recommended

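### Pressor-treated hypotension sits at Grade 2 in Table 9 and can be read as Grade 4 in Table 10, so DLT status near the end of infusion can depend on the label

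*Combined protocol and SAP*

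**What the plan says.** Section 6.1 sets the grading standard for DLTs: "All toxicities will be graded using CTCAE v 4.03". Item 1 of its non-hematologic list counts any related "≥Grade 3 non-hematologic toxicity, (excluding nausea, vomiting and/or diarrhea lasting <3 days and reversible with medical intervention". Item 4 covers cytokine release separately, at or above this grade: "Grade 3 flu-like symptoms or cytokine release symptoms that persist for >24 hours after study treatment administration despite symptomatic treatment".

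Two management tables attach grades to hypotension or to reactions that include it:

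- Table 9 (section 11.4.1, cytokine release; column headed as NCI CTCAE grade or severity) lists, for moderate Grade 2 hypotension, "Fluids and 1 dose of pressor (e.g. 0.3 mg epinephrine IM", and then modifications for later infusions.
- Table 10 (section 11.5, infusion reactions; column headed as NCI CTCAE grade) reads "Grade 4: Life-threatening; pressor or ventilatory support indicated". Its consequence is "Subjects who experience a Grade 4 reaction should be permanently discontinued from study".

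Table 12 (section 13.6), which gives the general CTCAE scale, describes Grade 2 in terms of limited, non-invasive measures. Its Grade 4 text has no pressor criterion.

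Hypotension is named as a cytokine release symptom ("nausea, vomiting, rash, tachycardia, hypotension and shortness of breath which usually presents several hours after the infusion") and also appears in the infusion reaction list in section 11.5. That section opens "While there is some overlap between infusion reactions symptoms and cytokine release symptoms". It then separates the two by when each typically occurs (during or after the infusion) and by mechanism.

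**The concern.** Under item 1 of section 6.1, the step from Grade 2 to Grade 3 or higher is the step from no DLT to DLT. If pressure falls around the end of an infusion and one pressor dose is given, a site using Table 9 finds that treatment under Grade 2. A site using Table 10 finds pressor support under Grade 4. The documents give no rule for choosing the label when timing is borderline, and mechanism cannot be read off at the bedside.

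At stake are the 3+3 count, whether the subject stays on treatment, the provision in section 11.8.2 that any Grade 4 toxicity may suspend the study, and the AE severity tables. Section 6 names transient hypotension as an expected event, safety and tolerability is the primary objective, and the study is multi-center, so sites can diverge.

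**Working it through.** **1. The plan's own figures.** At most two dose levels are tested (Dose Level 1, then either 2 or -1), each with 3 to 6 subjects: 2 × 3 = 6 and 2 × 6 = 12. This reproduces the 6-12 in section 14.3. The RP2D requires an observed DLT rate below 33%: 1/6 = 16.7% passes and 2/6 = 33.3% does not. This agrees with the Synopsis and section 6.

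**2. One borderline episode under each label.** Take related hypotension near the end of infusion, treated with fluids and one pressor dose.

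| | Read as cytokine release | Read as infusion reaction |
|---|---|---|
| Table used | Table 9 | Table 10 |
| Grade at which a pressor appears | 2 (one dose) | 4 (support indicated, life-threatening) |
| DLT under 6.1 item 1 | No | Yes, if graded 4 |
| Later treatment | Continues with modifications | Permanent discontinuation |

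The right-hand column applies only if the single dose is taken as pressor support and the episode as life-threatening. The documents do not say whether one dose counts.

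**3. Effect on the dose rule.** One relabelled subject turns 0/3 (escalate) into 1/3 (add three subjects), or 1/6 (level may be the RP2D) into 2/6 (previous level selected).

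**4. How often.** The documents give no rate for pressor-treated hypotension. Section 11.4.1 gives about 1% for Grade 3-4 hypotension, which is a different quantity. Let q be an assumed per-subject rate over the 28-day window. Then P(at least 1 of 3) = 1 − (1 − q)³, and P(at least 2 of 6) = 1 − (1 − q)⁶ − 6q(1 − q)⁵.

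| q (assumed) | At least 1 of 3 | At least 2 of 6 |
|---|---|---|
| 1% | 3.0% | 0.1% |
| 5% | 14.3% | 3.3% |
| 10% | 27.1% | 11.4% |
| 20% | 48.8% | 34.5% |

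These treat every pressor-treated episode as ambiguous, so they are upper illustrations. If q = 5% and one quarter of episodes are ambiguous (also assumed), the effective rate is 0.05 × 0.25 = 1.25%. The figures become 1 − 0.9875³ = 3.7% and 1 − 0.9875⁶ − 6 × 0.0125 × 0.9875⁵ = 0.2%.

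**5. Effect on clearing a level.** With per-subject DLT probability p, P(cleared) = (1 − p)³ + 3p(1 − p)²(1 − p)³. Assume a 10% DLT rate from other causes. If the episodes are not DLTs, P(cleared) = 0.729 + 0.3 × 0.59049 = 0.906. If all of them are DLTs and occur in different subjects from the other DLTs, p = 0.10 + q, and P(cleared) is 0.889, 0.814, 0.709 or 0.494 for q = 1%, 5%, 10% or 20%. This too is the extreme contrast, with every episode switching status.

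**6. A related gap in 6.1.** Item 4 requires cytokine release symptoms to last more than 24 hours. Item 1 has no such duration and does not exclude cytokine release. Grade 3-4 hypotension that resolves within 24 hours can therefore be read as a DLT under item 1 but falls outside item 4.

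**The case against.** The strongest reply is that one standard already governs. Section 6.1 names CTCAE v 4.03, and sections 9.1, 13.2 and 13.6 repeat it. Tables 9 and 10 are management guidance: the investigator grades first and then looks up the treatment. Table 9 does not say that giving one pressor dose makes an episode Grade 2. Table 10 Grade 4 also requires the reaction to be life-threatening and pairs pressor support with ventilation, while Table 9 itself separates one dose (Grade 2) from high-dose pressors (Grades 3 and 4). Dose decisions are taken by the sponsor with the investigators, so a site's label need not pass unreviewed.

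Much of this stands. A reader might infer that the protocol formally assigns one intervention to two grades, so that any pressor-treated episode is bound to be a DLT under one table and not under the other. The documents do not support that: one entry is a treatment and the other a description with a further condition. Nor can it be said that Table 10 reserves pressors for Grade 4, because its therapy lists are missing from the copy read. A reader might also take the ~1% in section 11.4.1 to depend on which table was used; that section does not say how those events were graded.

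The appeal to CTCAE does not close the gap. Both tables present their grades as CTCAE grades, and nothing says which prevails when they point different ways. Sponsor review helps only if there is a rule to review against.

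**Conclusion.** The inconsistency is real and feeds the DLT count, but it is limited to episodes whose label is unclear. For those, grade, DLT status under item 1 and discontinuation can turn on whether the event is called cytokine release or an infusion reaction. One such subject is enough to change a 3+3 decision.

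The frequency is unknown. The probabilities shown rest on assumed rates and on every pressor-treated episode being ambiguous. A reader might take them as the chance that the trial reaches a wrong dose decision; they are upper illustrations of how often the question could arise or, for clearing a level, of how far the two readings could differ. This is a should-fix clarification and does not show that the dose rule fails.

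**What to change.** Reconcile Tables 9, 10 and 12 with section 6.1:

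- State in 6.1 that DLT status for vasopressor-treated hypotension follows one grading standard, whichever label the episode carries.
- Make the grades in Tables 9 and 10 agree with that standard, and say whether a single pressor dose counts as pressor support.
- Say how items 1 and 4 of the non-hematologic list apply together to cytokine release symptoms.
- Record vasopressor use and its time relative to the infusion on the eCRF, so that the grade can be re-derived.

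Which grade and which management apply is for the sponsor to decide. The cost is wording in the tables and a line or two in 6.1. Treatments given for AEs and AE onset dates are already collected, so the added data item is the time of the vasopressor relative to the infusion.

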6 STUDY DESIGN AND TREATMENT PLAN

In this Phase 1, open-label, multi-center study, subjects with persistent, metastatic or recurrent squamous cell or non-squamous cell carcinoma, adenosquamous carcinoma, or adenocarcinoma of the cervix who have failed conventional therapy will receive the highest dose tolerated of ADXS11-001 infused intravenously (IV)

(± 10 minutes) with overall infusion volume of 250 mL on Day 1 of Weeks 1, 4, 7, and 10 of each 12-week cycle. Subjects must complete the prophylactic regimen at least prior to each ADXS11-001 infusion (as noted in Section 11.1) to mitigate and manage the potential immune response seen with immunotherapy administration.

Subjects who experience a DLT during the dose escalation portion of the study or experience events described as a DLT in any subsequent treatment cycle will be discontinued from study treatment. However, if the subject who experienced a DLT shows significant response to ADXS11-001, they may be eligible to receive ADXS11-001 at a lower dose level for subsequent doses and cycles following discussion and agreement between the Investigator and Sponsor. See Section 6.1 Dose Limiting Toxicity Criteria for definition of DLT.

The treatment to be used in this trial is outlined below in Table 4. Trial treatment should begin on the day of randomization or as close as possible to the date on which the treatment level is allocated/assigned.

Details on the dose calculation, preparation and administration are provided in the Pharmacy Manual.

Table 4 Trial Treatment

[figure not shown]
Dose Level	ADX11-001	Schedule
1	5 x 10 ⁹ CFU	Q3wks
2	$1 \times 10^{10} \text{CFU}$	Q3wks
-1	$1 \times 10^9 \text{CFU}$	Q3wks

ADXS11-001 will be given as a 3 weeks in repeating 12-week cycles

250 mL IV infusion every

A standard 3 + 3 design will be used in the dose escalation portion of the study. ADXS11-001 will be administered in sequential cohorts of 3-6 subjects, with a minimum of 48 hours between initial dosing for each of the first 3 subjects treated at each dose level. The first cohort will enroll a minimum of 3 subjects, according to a standard 3 + 3 design shown schematically in Figure 1.

Figure 1 3+3 Design Schematic

- Subjects in the first cohort will receive a dose of ADXS11-001 5 x 10⁹ CFU (Dose Level 1).
- If no DLTs are experienced in the 28 day DLT observation period at Dose Level 1, the next dose level of ADXS11-001 1 x 10¹⁰ CFU (Dose Level 2) will be explored.

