DLTs will only be assessed during the first 28 days in cycle 1 (See Section 6.1, Dose Limiting Toxicity Criteria, for DLT definition). Transient hypotension which may require IV fluids for management is an expected event that subjects may experience with ADXS11-001 infusions. Subjects with signs of cytokine release symptoms ≥Grade 3 (per CTCAE v 4.03) that persist for more than 24 hours despite symptomatic treatment, will be judged to have a DLT. Blood cultures will not be obtained on a routine basis but will be collected in subjects who have persistent fever 24 hours after the end of ADXS11-001 infusion. Subjects will receive a 7-day course of either oral 80 mg trimethoprim / 400 mg sulfamethoxazole once daily or 160 mg trimethoprim / 800 mg sulfamethoxazole (DS) 3 times over the course of the 7 days. Subjects with known allergy to sulfa drugs may receive ampicillin 500 mg 4 times daily for 7 days beginning on Day 4 (approximately 72) hours) after each study treatment infusion. A subject who experiences a fever (CTCAE Grade 1 or greater) 24 hours following the completion of ADXS11-001 infusion should be started on NSAIDS, hydration and other appropriate measures to treat the fever. In the event that the fever persists or worsens 48 hours following the completion of ADXS11-001 infusion then oral or broad spectrum IV antibiotics should be considered based on the subject's medical condition. If the fever remains unresponsive to oral/IV antibiotics 72 hours following the completion of the infusion then a blood culture should be obtained to evaluate for listeremia and determine the appropriate treatment course for the subject. Study cycles can be repeated at the RP2D (or less) for each subject until a discontinuation criterion is met. Criteria include documented disease progression, intolerable side effects not resolved with dose reduction or change in pre-medications, or the completion of 1 cycle of treatment post observation of complete response per RECIST 1.1 and immunerelated RECIST criteria (irCR).

Safety will be assessed by comparing treatment-related AEs, changes in physical examinations, vital sign measurements, and laboratory abnormalities.

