- Documentation of non-cancer surgeries, including, but not limited to artificial (prosthetic) joints, implants and/or devices, such as port/stent implant placed prior to study enrollment.
- Documentation of any on-study non-drug treatment and surgical procedures, including but not limited to artificial (prosthetic) joints, implants and/or devices.
- The pretreatment prophylactic regimen will be administered prior to and completed at least before each ADXS11-001 infusion.
- ADXS11-001 may be administered ± 7 days within Day 1 of each scheduled infusion. ADXS11-001 should not be administered less than 2 weeks apart without Sponsor approval.
- All subjects will receive a 7-day course of oral antibiotic therapy starting 72 hours after administration of ADXS11-001. All subjects will also receive an additional 6-month oral antibiotic course to be initiated 72 hours following the last dose of study treatment or upon discontinuation of study treatment.
- AEs and SAEs will be assessed from the time Informed Consent is obtained through the completion of the *Lm* surveillance period. All AE/SAEs will be followed through resolution. All AEs/SAEs experienced during this period must be recorded on the eCRF.
- Physical Examinations are to be completed prior to the ADXS11-001 administration to confirm safety criteria for study drug administration are met. PEs may be performed more frequently, as clinically indicated. Height will be measured at screening only. Weight will be collected prior to each ADXS11-001 infusion.
- Monitor vital signs every following the completion of every ADXS11-001 infusion.
- All laboratory procedures are to be completed and assessed by the investigator within 3 days prior to the administration of study treatment to confirm safety criteria for study treatment administration are met.
- 17 Coagulation profile will be assessed at screening only.
- A pregnancy tests must be performed within 72 hours prior to each ADXS11-001 infusion for female subjects of childbearing potential or less than 1 year postmenopausal. If the urine test is positive or cannot be confirmed as negative, a serum pregnancy test will be required.
- 19 Lm surveillance will include routine monitoring of CBC, CMP (including CRP, ESR) and blood cultures. Following completion of study treatment all assessments will be performed every 3 months (±2 weeks) for 3 years beginning 3 months after the subject's last dose of study treatment.

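### Section 6.1 sends DLTs to Table 11, whose hematologic row continues or restarts dosing after two DLTs for which Sections 6 and 11.6.2 require discontinuation

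*Combined protocol and SAP*

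**What the plan says.** Section 6.1 lists the DLT criteria and adds "Treatment modifications for DLT are shown in Table 11". Its hematologic list includes "Grade 4 hematologic toxicity" and "Grade 3 thrombocytopenia lasting >72 hours". Section 6 also says, in general terms, that treatment is modified according to Table 11.

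The consequence of a DLT is stated elsewhere. Section 6 says that subjects who have a DLT during escalation, or who later experience "events described as a DLT in any subsequent treatment cycle will be discontinued from study treatment". Section 11.6.2 repeats this rule. Both give one exception: a subject with a DLT who shows a significant response may continue at a lower dose level, after the Investigator and Sponsor agree.

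Table 11 covers drug-related adverse events. Its hematologic row does not hold treatment for Grades 1 to 3. For Grade 4 it holds treatment, restarts on recovery to Grade 1 or baseline, and discontinues only if recovery has not occurred within 12 weeks. The non-hematologic row is labelled as excluding cytokine release symptoms and DLTs; the hematologic row carries no such label. The sentence introducing the table rules out any change of dose.

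**The concern.** A site with a hematologic DLT that follows the reference in Section 6.1 arrives at a row that allows further dosing. A site that turns to Section 6 or 11.6.2 stops treatment. The protocol does not say which text prevails. Section 11.6.2 refers back to Section 6.1 for the DLT definition, and Section 6.1 sends the reader to Table 11 again.

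At stake is the safety of individual subjects, and consistent handling across sites, in a multi-center trial whose primary objective is safety and tolerability. Section 11.6.1 adds a smaller contradiction: it excludes any dose change, while Section 11.6.2 allows a lower dose for a responder.

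**Working it through.** The plan has no figure to reproduce here. The check sets each DLT in Section 6.1 against its Table 11 entry and against the rule in Sections 6 and 11.6.2.

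| DLT in Section 6.1 | Table 11 | Sections 6 and 11.6.2 | Result |
|---|---|---|---|
| Grade 4 hematologic toxicity (item 1; item 4, Grade 4 thrombocytopenia, is a subset) | Hold; restart at Grade 1 or baseline; stop only if not recovered within 12 weeks | Discontinue | Conflict |
| Grade 3 thrombocytopenia beyond 72 hours (item 3) | No hold | Discontinue | Conflict |
| Febrile neutropenia (item 2) | Depends on a grade that Section 6.1 does not give | Discontinue | Not counted |
| Non-hematologic DLTs (items 1 to 4) | No entry, because the row excludes DLTs | Discontinue | Pointer leads nowhere; no conflict |

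**Count.** Item 4 falls within item 1, and item 2 is left out for want of a grade. That leaves items 1 and 3: two distinct conflicts.

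**Do hematologic DLTs fall within Table 11?** Yes. The table is for drug-related events, and Section 6.1 requires a DLT to be at least possibly related to therapy. The DLT exclusion is written into one row only.

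**Does the responder exception reconcile the texts?** No. It needs a significant response, agreement of Investigator and Sponsor, and a lower dose. Table 11 requires none of these, and Section 11.6.1 keeps the dose unchanged.

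**How firm is the Grade 3 conflict?** Non-hematologic item 2 in Section 6.1 excludes transient Grade 3 laboratory abnormalities that reverse within 5 days without medical intervention, and it names hematologic values. It is unclear whether this overrides hematologic item 3. The two overlap for episodes longer than 72 hours and up to 5 × 24 = 120 hours, a band of 120 − 72 = 48 hours. Inside that band, an episode needing no intervention may not be a DLT. If the episode lasts longer than 5 days, or needs intervention, the exclusion cannot apply and the conflict stands on either reading.

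**Does the conflict affect dose finding?** No. An event within the 28-day window counts as a DLT whether or not the subject is dosed again. Cohort counts, escalation and the choice of RP2D are the same under both rules.

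**The case against.** The best defence is that Section 11.6.2 plainly governs. Its rule is specific to DLTs, mandatory, stated twice, and placed directly after Table 11. The table is titled as guidelines and introduced in permissive terms. The Sponsor takes escalation decisions with the Investigators, so each escalation DLT should reach the Sponsor. Much of this stands, and a careful reader would probably stop treatment. But Section 6.1 names Table 11 for DLTs in particular, and no precedence is stated. DLT-type events in later cycles do not enter an escalation decision, so that review would not necessarily catch them. If Table 11 was never meant for DLTs, the reference in Section 6.1 is still wrong.

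There are other safeguards. Laboratory results must be "assessed by the investigator within 3 days prior to the administration of study treatment to confirm safety criteria", and Section 13.8 requires the Investigator to find them acceptable before each dose. For Grade 4 events, Table 11 itself requires recovery before restart, and Section 11.8.2 permits suspension of the study. These reduce the risk. They do not remove it: after the first dose Section 13.8 re-applies only the hepatic and renal eligibility criteria, not the Table 3 platelet minimum of 75,000/mcL, and suspension under 11.8.2 is optional.

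A reader might go further and infer that a subject with a Grade 3 platelet DLT would be known as such before infusion 2 and then receive every remaining cycle 1 infusion. Infusions are given "on Day 1 of Weeks 1, 4, 7, and 10 of each 12-week cycle", so infusion 2 is nominally on Day (4 − 1) × 7 + 1 = 22, inside the 28-day window. The documents do not support the rest. Table 5 schedules no blood count between infusions 1 and 2 other than the pre-dose sample, taken on Day 22 − 3 = 19 at the earliest for a Day 22 infusion. One sample cannot show a duration beyond 72 hours, so unscheduled testing would be needed. The 5-day exclusion might also apply, and the Investigator would have to accept each later count.

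A reader might also infer that non-hematologic DLTs have no rule. They do, in Sections 6 and 11.6.2, and Tables 9 and 10 add guidance for cytokine release and infusion reactions. Only the reference in Section 6.1 fails.

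**Conclusion.** The inconsistency is in the current text and should be corrected. Two hematologic DLTs receive incompatible instructions: Grade 4 hematologic toxicity without qualification, and Grade 3 thrombocytopenia beyond 72 hours at least where the 5-day transient-laboratory exclusion does not cover it. For non-hematologic DLTs the fault is a reference with no target.

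The consequence is limited to possible re-dosing of a subject who should be off treatment, and to differences between sites. No rate is claimed: the visible text gives no frequency for these events, and Section 11.6 lists blood count changes only among the less likely adverse events. The conclusion assumes that Table 11 is read as printed, with the DLT exclusion confined to the non-hematologic row. If the exclusion was meant for the whole table, the hematologic conflict disappears but the reference in Section 6.1 still needs correcting.

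**What to change.** Three edits in the next amendment:

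1. In Section 6.1, replace the reference to Table 11 for DLT treatment modifications with a reference to Section 11.6.2.
2. In the Table 11 hematologic row, add *excluding DLTs and events described as a DLT in later cycles*. The non-hematologic row already excludes DLTs.
3. In Section 11.6.1, add *except as provided in 11.6.2* to the sentence that rules out dose changes.

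These make the rule already stated in Sections 6 and 11.6.2 the only one that applies to a DLT. Sample size, visits, DLT definitions and analyses do not change; the cost is the wording of one amendment.
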